8.4.6 Other clinical assessments

8.4.6.1 Body weight and height

The patient's body weight will be measured with light clothing and no shoes. If the patient has a prosthetic limb, this should be consistently worn during all weight measurements. The patient's height will be measured at Visit 1, with no shoes. The weight and height will be recorded in the eCRF.

8.5 Collection of adverse events

The Principal Investigator is responsible for ensuring that all staff involved in the study are familiar with the content of this section.

The definitions of an AE or SAE can be found in [Appendix B](#).

AE will be reported by the patient (or, when appropriate, by a caregiver, surrogate, or the patient's legally authorised representative).

The Investigator and any designees are responsible for detecting, documenting, and recording events that meet the definition of a SAEs and DAEs, amputation and events potentially placing the patient at risk for a lower limb amputation (preceding events). For information on how to follow-up AEs see Section [8.5.3](#).

8.5.1 Method of detecting AEs and SAEs

Care will be taken not to introduce bias when detecting SAEs or DAEs. Open-ended and non-leading verbal questioning of the patient is the preferred method to inquire about AE occurrences.

Safety information on SAEs and DAEs, amputations, adverse events (AEs) leading to amputation and potential risk factor AEs for amputations affecting lower limbs will be collected and entered into eCRFs by site personnel according to the study visit schedule.

If the potential efficacy event fulfils SAE criteria (see [Appendix B 2](#)) the site is to record and report these events to the Sponsor or designee within timelines described in [Section 8.6.1](#).

8.5.1.1 Adverse events (AEs) leading to amputation and potential risk factor AEs for amputations affecting lower limbs (“preceding events”)

To ensure that data on amputations is systematically collected, amputations and underlying conditions relevant to amputation will be recorded on a specific eCRF page. The adverse event leading to amputation should be recorded in the eCRF as AE/SAE.

In addition to amputation, non-serious and serious events potentially placing the patient at risk for a lower limb amputation (“preceding events”) should also be recorded in the eCRF as AE/SAE whether or not an amputation has taken place. The lower limb amputation “preceding events” of interest include diabetic foot related conditions, vascular, volume depletion, wounds/injury/trauma, infection and neuropathy. If any of these or other potentially relevant events have occurred, relevant information must be provided (this will be collected on a dedicated eCRF page - for details see eCRF instruction”).

8.5.1.2 Capture of DKA events

For SAEs or DAEs reported by the Investigator as Diabetic Ketoacidosis (DKA - see definition below) additional information will be recorded on specific eCRF pages in addition to the AE/SAE form. All potential events of DKA will be submitted to an independent DKA Adjudication Committee, see [Section 8.5.1.2.2](#))

8.5.1.2.1 DKA definition

A diagnosis of Diabetic Ketoacidosis should only be made in a clinical setting consistent with DKA (based on patient history, symptoms, and physical exam) and in the absence of more likely alternative diagnoses and causes of acidosis (such as lactic acidosis). The following biochemical data should support diagnosis:

- Ketonaemia ≥ 3.0 mmol/L and/or significant ketonuria (more than 2+ on standard urine sticks)
- At least one of the following criteria suggesting high anion gap metabolic acidosis:
 - Arterial or Venous pH ≤ 7.3
 - Serum bicarbonate ≤ 18 mEq/L
 - Anion gap $[\text{Na} - (\text{Cl} + \text{HCO}_3)] > 10$

8.5.1.2.2 Diabetic Ketoacidosis Adjudication Committee T2D

All potential events of DKA will be submitted to an independent DKA Adjudication Committee. The committee will be kept blinded to the treatment codes. A separate DKA Adjudication Manual will define and describe the procedures for the collection of DKA information, handling, adjudication criteria and reporting of these events.

8.5.1.3 Capture of cardiac ischaemic events and stroke

For myocardial infarctions, unstable angina and stroke additional information will be recorded on specific eCRF pages in addition to the AE/SAE form.

The diagnosis of stroke, MI and unstable angina should be made according to standard clinical practice and align with the definition for stroke in the standardised definitions for endpoints ([Hicks et al 2018](#)) described in [Appendix C](#).

8.5.1.4 Capture of Major hypoglycaemic events

A major hypoglycemic event is defined as an event that is characterized by altered mental and/or physical status, any symptoms of severe impairment in consciousness or behavior, that require external assistance of another person for treatment of hypoglycemia and recovery, to actively administer carbohydrates, glucagon, or take other corrective actions.

Plasma glucose concentrations may not be available during a hypoglycaemic event, but neurological recovery following the corrective actions is considered sufficient evidence that the event was induced by a low plasma glucose concentration. Major hypoglycaemic episodes will be recorded in the eCRF as an AE and on an additional eCRF page.

8.5.1.5 Capture of additional laboratory values

Any additional safety laboratory assessments during the study period, including creatinine, will be obtained per the Investigator's medical judgment in the course of standard care using local laboratories. Laboratory values would be recorded only on SAE eCRFs as part of narrative information, per the Investigator's judgment.

8.5.2 Time period and frequency for collecting AE and SAE information

Non-serious adverse events as defined per protocol will be collected from randomisation (Visit 2), throughout the treatment period until and including the patient's last visit (the study closure visit). Serious adverse events are recorded from the time of signing of informed consent form throughout the treatment period until and including the patient's last visit.

All SAEs will be recorded and reported to the sponsor or designee within 24 hours, as indicated in [Appendix B](#). The Investigator will submit any updated SAE data to the sponsor within 24 hours of it being available.

The method of recording, evaluating, and assessing causality of AE and SAE and the procedures for completing and transmitting SAE reports are provided in [Appendix B](#).

8.5.3 Follow-up of AEs and SAEs

After the initial AE/SAE report, the Investigator is required to proactively follow each patient at subsequent visits/contacts. All SAE and events of amputation and potential preceding events will be followed until resolution, stabilization, the event is otherwise explained, or the patient is lost to follow-up.

Any AEs that are unresolved at the patient's last visit in the study are followed up by the Investigator for as long as medically indicated, but without further recording in the CRF. AstraZeneca retains the right to request additional information for any patient with ongoing AE(s)/SAE(s) at the end of the study, if judged necessary.

8.5.4 Adverse event data collection

The following variables will be collect for each AE;

- AE (verbatim)
- The date when the AE started and stopped
- Maximum intensity (mild/moderate/severe)
- Whether the AE is serious or not
- Investigator causality rating against the Investigational Product(s) (yes or no)
- Action taken with regard to IP
- Outcome

In addition, the following variables will be collected for SAEs:

- Date AE met criteria for serious AE
- Date Investigator became aware of serious AE
- AE is serious due to
- Date of hospitalisation
- Date of discharge
- Probable cause of death
- Date of death
- Autopsy performed
- Causality assessment in relation to Study procedure(s) and/or other medication
- Description of AE

8.5.5 Causality collection

The Investigator will assess causal relationship between the IP and each AE and answer ‘yes’ or ‘no’ to the question ‘Do you consider that there is a reasonable possibility that the event may have been caused by the investigational product?’

For SAEs, causal relationship will also be assessed for other medication and study procedures. Note that for SAEs that could be associated with any study procedure the causal relationship is implied as ‘yes’.

A guide to the interpretation of the causality question is found in [Appendix B](#) to the Clinical Study Protocol.

8.5.6 Adverse events based on signs and symptoms

All AEs spontaneously reported by the patient or reported in response to the open question from the study personnel: ‘Have you had any health problems since the previous visit/you were last asked?’ or revealed by observation will be collected and recorded in the eCRF if they fulfil the criteria specified in Section 8.5.2. When collecting AEs, the recording of diagnoses is preferred (when possible) to recording a list of signs and symptoms. However, if a diagnosis is known and there are other signs or symptoms that are not generally part of the diagnosis, the diagnosis and each sign or symptom will be recorded separately.

8.5.7 Adverse events based on examinations and tests

The results from the Clinical Study Protocol mandated vital signs and laboratory values will be summarised in the clinical study report. Deterioration as compared with baseline in protocol-mandated vital signs should therefore only be reported as AEs if they fulfil any of the SAE criteria or are the reason for discontinuation of treatment with the IP. If deterioration in a vital sign is associated with clinical signs and symptoms, the sign or symptom will be reported as an AE if they

fulfil any of the SAE criteria or are the reason for discontinuation of treatment of IP, and the associated vital sign will be considered as additional information.

8.5.8 Disease-under study (DUS) (not applicable)

8.5.9 Disease progression (not applicable)

8.6 Safety reporting and medical management

8.6.1 Reporting of serious adverse events

All SAEs have to be reported, whether or not considered causally related to the investigational product, or to the study procedure(s). All SAEs will be recorded in the eCRF.

If any SAE occurs in the course of the study, then Investigators or other site personnel inform the appropriate AstraZeneca representatives within one day i.e., immediately but **no later than 24 hours** of when he or she becomes aware of it.

The designated AstraZeneca representative works with the Investigator to ensure that all the necessary information is provided to the AstraZeneca Patient Safety data entry site **within 1 calendar day** of initial receipt for fatal and life-threatening events **and within 5 calendar days** of initial receipt for all other SAEs.

For fatal or life-threatening adverse events where important or relevant information is missing, active follow-up is undertaken immediately. Investigators or other site personnel inform AstraZeneca representatives of any follow-up information on a previously reported SAE within one calendar day i.e., immediately but **no later than 24 hours** of when he or she becomes aware of it.

Once the Investigators or other site personnel indicate an AE is serious in the EDC system, an automated email alert is sent to the designated AstraZeneca representative.

If the EDC system is not available, then the Investigator or other study site staff reports a SAE to the appropriate AstraZeneca representative by telephone.

The AstraZeneca representative will advise the Investigator/study site staff how to proceed.

Investigators or other site personnel send relevant CRF modules by fax to the designated AstraZeneca representative.

For further guidance on the definition of a SAE, see [Appendix B](#) of the Clinical Study Protocol.

8.6.1.1 Reporting of SAEs considered to be potential endpoints

In order to avoid unnecessary unblinding of efficacy endpoint events, certain SAEs which are also potential endpoints (i.e., fatal AEs and HF events) will not be reported to health authorities. Clinical data for the above mentioned events will be recorded as AEs/SAEs as well as on separate event forms in the eCRF. Recording of a suspected endpoint should be done within the same timeframes as defined for SAEs (see Section [8.6.1](#)).

In addition, fatal AEs and potential HF endpoints will be centrally adjudicated by an independent CEA committee (see Section 8.3.1 and 8.3.2). If adjudication confirms the endpoint, the SAE will not be reported to health authorities. However, if it is determined by the CEA committee that a potential endpoint does not meet the endpoint criteria, the event will be reported (according to the timelines specified in Section 8.6.1) to AZ patient safety data entry site and if applicable to the health authorities (note that the clock starts when the adjudication results are available).

8.6.2 Pregnancy

All pregnancies and outcomes of pregnancy should be reported to AstraZeneca except if the pregnancy is discovered before the study patient has received any IP. If a pregnancy is reported, the Investigator should inform the sponsor within 24 hours of learning of the pregnancy. Abnormal pregnancy outcomes (e.g. spontaneous abortion, foetal death, stillbirth, congenital anomalies, ectopic pregnancy) are considered SAEs.

8.6.2.1 Maternal exposure

Women of childbearing potential who are not using contraception as defined in Section 5.2; exclusion criterion number 18 are not allowed to be included in this study. Should a pregnancy still occur, the investigational product should be discontinued immediately and the pregnancy reported to AstraZeneca.

Dapagliflozin must not be used in the second and third trimesters of pregnancy. In the time period corresponding to second and third trimester of pregnancy with respect to human renal maturation, maternal exposure to dapagliflozin in rat studies was associated with increased incidence and/or severity of renal pelvic and tubular dilatations in progeny.

There are no adequate and well-controlled studies of dapagliflozin in pregnant women. When pregnancy is detected, investigational product(s) should be discontinued.

8.6.3 Overdose

Dapagliflozin has been well tolerated at doses of up to 500 mg/day in single dose testing in healthy volunteers and up to 100 mg/day in repeat dose testing for 14 days in healthy volunteers and patients with T2D. Suspected single intake of more than 50 tablets of 10 mg dapagliflozin tablets or repeated intake of more than 10 tablets of 10 mg dapagliflozin tablets should be reported on the eCRF overdose module. If an overdose is suspected, monitoring of vital functions as well as treatment should be performed as appropriate.

For further information regarding overdose, refer to the IB.

- An overdose without associated symptoms is only recorded on the Overdose eCRF module
- An overdose with associated AEs is recorded as the AE diagnosis/symptoms on the relevant AE modules in the eCRF and on the Overdose eCRF module

If an overdose on an AstraZeneca IP occurs in the course of the study, then the investigator or other site personnel inform appropriate AstraZeneca representatives immediately, or no later than 24 hours of when he or she becomes aware of it.

The designated AstraZeneca representative works with the investigator to ensure that all relevant information is provided to the AstraZeneca Patient Safety data entry site.

For overdoses associated with a SAE, the standard reporting timelines apply, see Section 8.5.2. For other overdoses, reporting must occur within 30 days.

8.7 Pharmacokinetics (not applicable)

8.8 Pharmacodynamics (not applicable)

8.9 Optional exploratory genetics

Approximately 6 mL blood sample for DNA isolation will be collected from subjects who have consented to participate in the genetic analysis component of the study. Participation is optional. Subjects who do not wish to participate in the genetic research may still participate in the study.

See [Appendix D](#) for Information regarding genetic research. Details on processes for collection and shipment and destruction of these samples can be found in [Appendix D](#).

8.10 Biomarkers (not applicable)

8.11 Health Economics (not applicable)

9. STATISTICAL CONSIDERATIONS

9.1 Statistical hypotheses

For the primary and secondary endpoints, the following hypothesis will be tested at the 4.980 % 2-sided level:

H0: HR [dapagliflozin:placebo] =1

versus

H1: HR [dapagliflozin:placebo] ≠1

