9.2 Sample size determination

The primary objective of the study is to determine the superiority of dapagliflozin versus placebo added to standard of care in reducing the composite of CV death and heart failure events (hospitalisation for HF or urgent HF visit). Two hypotheses will be tested simultaneously (i.e., dual primary analyses) for the primary objective: (1) in the full population and in (2) an LVEF <60% subpopulation, with alpha allocated to each test. Originally, assuming a true hazard ratio (HR) of 0.80 between dapagliflozin and placebo, using a two-sided alpha of 5%, 844 primary endpoint

events were targeted in order to provide a statistical power of 90% for the test of the primary composite endpoint. To allow testing for the dual primary analyses, alpha will be allocated to each test to ensure strong control of the overall type I error rate. The target number of patients with a primary endpoint has been increased to 1117 in order to provide adequate statistical power for each test. It is anticipated that at least 70% of the events (i.e., approximately 780 events) will be available for the LVEF <60% subpopulation. To illustrate, assuming a true HR of 0.80, a two-sided alpha of 2.4% allocated to the LVEF <60% subpopulation will result in a power of 80% to detect a treatment difference, whereas an alpha allocation of 1.5% to the full population will result in 90% power. The final alpha split for the dual primary analyses will be specified in the SAP prior to the planned interim analysis. This is based on an overall 1:1 allocation between dapagliflozin and placebo.

The HR 0.80 was originally chosen as a conservative assumption based on the observed HR 0.72 (95% confidence interval 0.50-1.04) for the composite of HF hospitalisation and CV death in patients with HF at baseline in the EMPA-REG OUTCOME trial ([Fitchett et al 2016](#)) and HR 0.61 (0.46-0.80) for patients with history of HF in the CANVAS program ([Rådholm et al 2018](#)) considering that these were post-hoc analyses in subgroups with limited documentation of baseline HF diagnosis, not characterised by ejection fraction.

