9.4.1 Efficacy analyses

9.4.1.1 Analysis of the primary variable

The primary variable is the time from randomisation to first event included in the primary composite endpoint. Two hypotheses will be tested simultaneously (i.e., dual primary endpoint analyses): (1) in the full population and (2) in an LVEF <60% subpopulation, with alpha allocated to each test. The primary analysis will be based on the ITT principle using the FAS, including events occurring on or prior to the PACD, adjudicated by the CEA committee.

In the analysis of the primary composite endpoint, treatments (dapagliflozin versus placebo) will be compared using a Cox proportional hazards model with a factor for treatment group, stratified by T2D status at randomisation. The p-value, HR and 95% confidence interval will be reported.

The contribution of each component of the primary composite endpoint to the overall treatment effect will be examined. Methods similar to those described for the primary analysis will be used to separately analyse the time from randomisation to the first occurrence of each component of the primary composite endpoint. HR and 95% confidence intervals will be reported.

Kaplan-Meier estimates of the cumulative incidence to the first occurrence of any event in the primary endpoint will be calculated and plotted, for overall analysis and for the individual components.

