9.4.1.2 Analysis of the secondary variables

The outcome of all HF events (first and recurring) and CV death will be analysed by the semi-parametric proportional rates model (Lin et al 2000) to test the treatment effect and to quantify the treatment difference. The rate ratio and its 95% confidence interval and corresponding two-sided p-value will be presented. This outcome will also be analysed for the LVEF <60% subpopulation within the multiple testing procedure as described in Section 9.2.

The analysis of change from baseline for KCCQ total symptom score at 8 months will be further detailed in the statistical analysis plan, e.g. with consideration of handling of patients who die. In addition to the secondary endpoint, total symptom score, the overall summary score, clinical summary score and domain scores will be analysed. A responder analysis will also be performed (more details presented in the SAP).

The analysis of the endpoints time from randomisation to CV death and time to all-cause mortality will be analysed in the similar manner as the primary variable.

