9.4.3 Methods for multiplicity control

A closed testing procedure including a pre-specified hierarchical ordering of the primary and secondary endpoints will be utilised. The Type I error will be controlled at an overall two-sided 5% level for multiplicity across primary and secondary endpoints and in consideration of the planned interim analysis. With one interim analysis at 67% of events (see Section 9.5) the two-sided significance level in final analysis, α , will be 4.980%. Statistical significance will be assessed in two branches in a pre-specified order of the endpoints and populations which is further described in the SAP. The significance level α , will be split for the two primary analyses, denoted α_1 and α_2 . If either of the tests of the primary endpoint in the full study population and for LVEF <60% subpopulation is significant at respective levels α_1 and α_2 , the next hypothesis in the respective branch sequence will be tested at the same significance level. The exact split of alpha will be documented in an updated SAP before the interim analysis. If all hypotheses in one arm are rejected, the alpha will be recycled to the other branch.

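### Section 9.1 gives 4.980% as the level of each primary and secondary test, while Section 9.4.3 makes 4.980% a total to be split between two primary tests

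*Protocol*

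**What the plan says.** Section 9.1 of the protocol consists of one sentence and one pair of hypotheses. The sentence reads "For the primary and secondary endpoints, the following hypothesis will be tested at the 4.980 % 2-sided level". The null is HR = 1 for dapagliflozin against placebo. No population is named, no split is mentioned, and there is no reference to Section 9.4.3.

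Section 9.4.3 uses the same number differently. There 4.980% is the two-sided level left for the final analysis after one interim, and it "will be split for the two primary analyses" as alpha_1 and alpha_2. When a primary test succeeds, "the next hypothesis in the respective branch sequence will be tested at the same significance level". A share moves across only at the end of a branch: "If all hypotheses in one arm are rejected, the alpha will be recycled to the other branch".

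The other statistical sections side with 9.4.3. Section 9.2 says that "alpha will be allocated to each test to ensure strong control of the overall type I error rate". Section 9.4.1.1 describes two simultaneous primary tests "with alpha allocated to each test", and the synopsis says the same.

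For the first secondary endpoint, total HF events and CV death, Section 9.4.1.2 specifies a proportional rates model: "The rate ratio and its 95% confidence interval and corresponding two-sided p-value will be presented". The next secondary endpoint in Table 3 is a change from baseline in KCCQ total symptom score.

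**The concern.** The two sections give different answers to the question of what level decides whether a primary test is positive. Under 9.4.3 neither primary test starts at 4.980%. A test can reach that level only after every hypothesis in the other branch has been rejected. Section 9.1 gives 4.980% to the test outright.

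The section headed as the statement of hypotheses also leaves out the second primary hypothesis, although the primary objective names both populations. Its wording would suit a design with one primary test.

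At stake is the 5% overall type I error promised in 9.4.3. Following 9.4.3 keeps it. Applying 9.1's level to both primary tests does not.

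A smaller point is that 9.1 applies its HR null to all secondary endpoints. A rate ratio and a difference in a symptom score are not hazard ratios.

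**Working it through.** **Inputs from the protocol.** Final level 4.980% and overall 5% (9.4.3); interim at 0.2% two-sided with about 67% of events, in the full population (9.5); 1117 events in total, about 780 in LVEF <60%, true HR 0.80, 1:1 allocation, illustrative levels of 1.5% (full) and 2.4% (LVEF <60%) with stated powers of 90% and 80% (9.2).

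**1. Is 4.980% a total or a per-test level?** With the interim and final statistics bivariate normal and correlation √(information fraction), solve for the final level that gives 5% overall after an interim at 0.2%. The result is 4.980% at a fraction of 2/3 and 4.981% at 0.67. The protocol's number is reproduced as the whole alpha left for the final analysis of one hypothesis. With two primary hypotheses it is the amount to be shared.

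**2. Which level do the stated powers use?** Power = Φ(√D/2 × |ln 0.80| − z), where z is the two-sided critical value and D the number of events.

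| Population | D | √D/2 × 0.2231 | Level | z | Power |
|---|---|---|---|---|---|
| Full | 1117 | 3.729 | 1.5% | 2.432 | 90.3% (stated 90%) |
| Full | 1117 | 3.729 | 4.980% | 1.962 | 96.1% |
| LVEF <60% | 780 | 3.116 | 2.4% | 2.257 | 80.5% (stated 80%) |
| LVEF <60% | 780 | 3.116 | 4.980% | 1.962 | 87.6% |

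The stated powers match the split levels and do not match 4.980%. The event target was therefore built on the reading in 9.4.3.

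**3. Family-wise error if 9.1's level is used for both primary tests.** Under the global null the two final statistics are bivariate normal with correlation √(event share of the subpopulation). Error = 1 − P(|Z_full| < z₁ and |Z_sub| < z₂). Section 9.2 sets only a floor for the share ("It is anticipated that at least 70% of the events"), so a range is shown.

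| Event share | Correlation | Both at 4.980% | 1.5% and 2.4% |
|---|---|---|---|
| 70% | 0.837 | 7.5% | 3.1% |
| 80% | 0.894 | 7.1% | 2.9% |
| 90% | 0.949 | 6.5% | 2.7% |

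These are final-analysis figures. A simulation of 4 million draws at 780/1117 events, with the interim included, also gives 7.5% for both tests at 4.980%. The figure of 7.5% is the top of the range, because a larger share brings the two tests closer together.

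**4. What this means for the observed effect.** The least favourable HR that still reaches significance is exp(−2z/√D).

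- Full population: exp(−2 × 1.962/√1117) = 0.889 at 4.980%; exp(−2 × 2.432/√1117) = 0.865 at 1.5%.
- LVEF <60%: exp(−2 × 1.962/√780) = 0.869 at 4.980%; exp(−2 × 2.257/√780) = 0.851 at 2.4%.

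An observed HR between the two values is positive under 9.1 and, before any recycling, negative under the illustrative split.

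**The case against.** The strongest reply is that the governing rule is clear. Section 9.4.3 defines 4.980% as the total and sets out split, branches and recycling; the synopsis, 9.2 and 9.4.1.1 agree; the power figures rest on split levels. No statistician could take the decision level from 9.1 without ignoring these sections, and 9.1 can charitably be read as giving the level for the whole family. The agreement elsewhere is real, and it is why this is a fault of wording and not of the procedure. The charitable reading is strained, because 9.1 says the hypothesis is tested at that level.

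A second reply is that 7.5% describes no procedure in the protocol. It takes two tests from 9.2 and the level from 9.1. That is fair: the figure is conditional on a misreading and does not describe the planned analysis.

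Third, the contrast with 3.1% is partly due to the illustration, since 1.5% + 2.4% = 3.9% leaves some of the 4.980% unspent. An even split of 2.49% each (an assumption) gives 3.9%, 3.6% and 3.3% at event shares of 70%, 80% and 90%. This narrows the gap but still leaves the error below 5%, against 6.5% to 7.5%.

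Fourth, both primary hypotheses appear in 2.1, Table 3, 9.2 and 9.4.1.1, and nobody would test a KCCQ change as a hazard ratio. Both statements are true. They make the correction easy but do not make 9.1 right as written.

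**Conclusion.** The concern holds. Section 9.1 states the wrong level for the individual tests, omits the second primary null, and gives a null that does not fit two of the secondary endpoints. The number 4.980% is correct, but only as the total for the final analysis. The procedure in 9.4.3 stands, and leaving the exact split to the SAP is proper.

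The size is conditional: a family-wise error of 6.5% to 7.5% for the two primary tests if 9.1's level were applied to both. This rests on the normal approximation, the global null, and an event share between 70% and 90% for the subpopulation. The critical HRs at the split levels are illustrations, because the final split is not in the protocol. The point should be fixed because it concerns the threshold for primary success, but it does not call the design into question.

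**What to change.** Rewrite Section 9.1 along these lines:

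- Two primary nulls: HR = 1 in the full population and HR = 1 in the LVEF <60% subpopulation, tested at alpha_1 and alpha_2 under Section 9.4.3.
- 4.980% described as the total two-sided level for the final analysis, with a note that a remaining hypothesis reaches a higher level than its branch's share only through the recycling in 9.4.3.
- Secondary nulls on their own scales: rate ratio = 1 for total HF events and CV death; no treatment difference for KCCQ total symptom score; HR = 1 for CV death and for all-cause death.

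The exact split may stay in the SAP. The cost is two or three sentences, with no change to data collection, sample size or the testing procedure.
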